2.14 Other exploratory analyses

MMR rate at 24 weeks

The FAS will be used for the following exploratory analyses:

1. A logistic regression model adjusted for the stratification factor (based on the randomization platform data IRT) will be fit to assess treatment effect. An adjusted odds ratio for the treatment effect with associated 95% confidence intervals will be presented. Mantel-Haenszel estimates of the common odds ratio and the corresponding 95% confidence interval will also be provided.
Some subjects were mistratified. To assess the impact of this mistratification on the treatment effect assessment, a logistic regression adjusting for major cytogenetic status at baseline based on CRF data will also be run.
2. Based on the subgroups specified in [Section 2.2.1](#), the following analyses will be performed for each subgroup:
 - Proportion of patients with MMR at 24 weeks and its 95% confidence interval based on the Pearson-Clopper method within each treatment group
 - The difference in MMR rate at 24 weeks between treatment groups and the corresponding Wald 95% confidence interval

Efficacy analyses in subgroups will be purely exploratory and are intended to explore the consistency of treatment effect. Forest plot (n, risk difference, Wald 95% confidence interval) will be produced to graphically depict the treatment effect estimates in different subgroups. No inferential statistics (p-values) will be produced for the subgroups.

Post-hoc exploration of the treatment effect in different subgroups and assessment of the possible effect of differences in distribution of baseline characteristics were conducted (e.g. distribution of reasons for discontinuation of last prior TKI by gender and treatment, distribution of MCyR status at baseline by reasons for discontinuation of last prior TKI, distribution of mutation status at Week 1 Day 1 by reasons for discontinuation of last prior TKI).

3. A logistic regression model adjusted for the stratification factor (baseline major cytogenetic response status based on randomization data) and other important variables identified by the subgroup analyses above will be fit to assess treatment effect. An adjusted odds ratio for the treatment effect with associated 95% confidence intervals will be presented.
To assess the impact of mistratifications on the treatment effect assessment, the same analysis will be repeated, adjusting for major cytogenetic status at baseline based on CRF data instead of based on randomization data.

Influence of early molecular response levels on long term molecular response levels

The relationship between MMR status at 24 weeks and MMR status at 48 and 96 weeks will be explored using FAS by reporting contingency tables and by applying a logistic regression including treatment group, MMR status at 24 weeks and their interaction as covariates. Treatment group will be included in this summary table. The odds ratios between treatment groups with 95% confidence intervals will be reported, for each category of MMR status at 24 weeks and overall. If the interaction of treatment by MMR status at 24 weeks is significant (e.g. when $p < 0.1$), overall odds ratio for treatment will not be reported.

Efficacy Analysis on Switch Analysis Set

Efficacy analyses on the Switch Analysis Set will be performed at the time of the 96-week analysis. Unless otherwise specified, endpoints are defined and analyzed similarly as specified in Sections 2.5, 2.6, and 2.7 on Switch Analysis Set, but with baseline, FD, LD, and EoT replaced by baseline_switch, FD_{switch}, LD_{switch}, and S-EoT. The below are the efficacy endpoints to be analyzed:

- MMR rate at and by all protocol-planned visits.
- CCyR rate at and by all protocol-planned visits.
- Time to MMR
- Duration of MMR
- Time to CCyR
- Duration of CCyR
- Time to Treatment Failure

The analysis of time-to-event endpoints will be conducted only if at least 5 events are observed.

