2.5 Analysis of the primary objective/estimand

In this section, the targeted treatment effect corresponding to the primary objective as well as the primary objective is clarified using the estimand language.

The primary clinical question of interest is: Is the efficacy of asciminib (40 mg bid) superior to bosutinib (500 mg qd) in CML patients in chronic phase, previously treated with 2 or more tyrosine kinase inhibitors, with regards to achieving MMR at 24 weeks while on study treatment and without meeting any treatment failure criteria (defined in [section 5.4.4](#)) prior to 24 weeks, regardless of dose modification, dose interruption, or deviation in any intake of concomitant medications.

The primary estimand is described by the following attributes:

Population: CML patients in chronic phase, previously treated with 2 or more tyrosine kinase inhibitors. Further details about the population are provided in Section 5 of the protocol.

Endpoint: Major Molecular Response (MMR) achieved at 24 weeks while on study treatment without meeting any treatment failure criteria (defined in [section 5.4.4](#)) prior to 24 weeks. A patient will be counted as having achieved MMR at 24 weeks if he/she meets the MMR criterion (BCR-ABL ratio $\leq 0.1\%$) at 24 weeks while on study treatment unless the patient met any treatment failure criteria (defined in [section 5.4.4](#)) prior to 24 weeks.

Intercurrent events:

- Treatment discontinuation (i.e. having performed an EOT visit) prior to 24 weeks due to any reason (e.g. intolerance, treatment failure, death, etc.): non response
- Meeting any treatment failure criteria (defined in [section 5.4.4](#)) prior to 24 weeks: non response
- Dose modification, dose interruption, or deviation in any intake of concomitant medications: ignore (treatment policy strategy)

Treatment of interest: the randomized treatment (the investigational treatment asciminib or the control treatment bosutinib) received for at least 24 weeks with or without dose modification, dose interruption or deviation in any intake of concomitant medications. Further details about the investigational treatment and control treatment are provided in Section 6 of the protocol.

Handling of remaining intercurrent events : no other IE foreseen

The summary measure: difference in MMR rate and its 95% confidence interval at week 24 between the two treatment arms.

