3.1 Primary analysis

To test the null hypothesis that the MMR rate at 24 weeks is equal in the two treatment arms, based on two-sided 5% level of significance and with 90% power, 222 patients will be needed in total (i.e. 148 patients in the asciminib arm and 74 patients in the bosutinib arm based on 2:1 randomization allocation). The calculations were made using the software package PASS (2008).

It is assumed that asciminib leads to a 20% improvement in the MMR rate at 24 weeks over bosutinib from 15% to 35% which corresponds to an odds ratio of 3.05. The assumed bosutinib MMR rate of 15% at 24 weeks is based on previous trials evaluating bosutinib therapy ([Kuoury et al. 2012], [Gambacorti-Passerini et al. 2014], [García-Gutiérrez et al. 2015]).

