3.2 Power for analysis of key secondary variables

If the primary analysis of MMR rate at 24 weeks is statistically significant, then the key secondary endpoint MMR rate at 96 weeks will be tested, with the overall alpha controlled at the 5% two-sided level using a gatekeeping strategy.

Table 3-1 below summarizes the treatment effects of the key secondary endpoint which can be detected with 80% and 90% power, based on the specified assumptions regarding the bosutinib effect. The calculations were made using the software package PASS (2008).

Table 3-1 Detectable effect sizes for key secondary endpoint

Endpoint	Anticipated effect with bosutinib	2-sided alpha	Power	Detectable effect size [§]
MMR rate at 96 weeks	30% [*]	0.05	90%	≥ 23%
			80%	≥ 20%

*: [Gambacorti-Passerini et al. 2014], Figure 1D.

§: Absolute difference from the anticipated effect with bosutinib.

For MMR rate at 96 weeks, if the anticipated effect with bosutinib is 30%, then the given sample size with 2-sided alpha=0.05 would allow to detect an absolute difference of at least 23% (i.e. MMR rate at 96 weeks with asciminib is at least 53%) for 90% power and of at least 20% (i.e. MMR rate at 96 weeks with asciminib is at least 50%) for 80% power.

4 Change to protocol specified analyses

Pharmacokinetic analysis set: Removal of the condition related to vomiting to consider a concentration evaluable as the occurrence and time of vomiting is not collected in the CRF.

The estimand language was implemented in sections 2.5 and 2.6. Then, the PPS and analyses based on PPS were removed.

The subgroup considering historical BCR-ABL1 mutations was removed as not considered clinically relevant.

A definition for loss of CHR was provided.

Definition of loss of MMR: removed any reference to confirmation of CHR and CCyR as confirmation of CHR and CCyR was not mandated by protocol and was therefore not performed in practise.

The following analyses were added:

ECOG status, time to event analyses for duration of MMR and CCyR, exposure adjusted AE incidence and yearly AE incidence, COVID-19 related sensitivity analyses.

5 Appendix

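### Section 2.14 compares asciminib with bosutinib within Week 24 MMR categories: not a randomized comparison, biased in a direction the documents do not fix, and not the early-to-late association the analysis is about

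*Combined protocol and SAP*

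**What the plan says.** The subsection of SAP Section 2.14 on early and long-term molecular response uses the full analysis set. It plans contingency tables of Week 24 MMR status against Week 48 and Week 96 MMR, with treatment group shown, and a "logistic regression including treatment group, MMR status at 24 weeks and their interaction as covariates". The effect estimates it names are treatment contrasts: "The odds ratios between treatment groups with 95% confidence intervals will be reported, for each category of MMR status at 24 weeks and overall". The overall treatment odds ratio is withheld if the interaction is significant, with p < 0.1 given as the example. No odds ratio for Week 24 MMR itself is named, and nothing warns that these contrasts are not randomized.

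Section 2.5 makes Week 24 MMR the primary endpoint and sets this rule for patients who stop early: "Treatment discontinuation (i.e. having performed an EOT visit) prior to 24 weeks due to any reason (e.g. intolerance, treatment failure, death, etc.): non response". Section 2.6 applies the same rule at Week 96. Section 3.1 assumes a change relative to "bosutinib from 15% to 35% which corresponds to an odds ratio of 3.05".

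**The concern.** Reporting a treatment effect by category, with a check on the interaction, suits a baseline characteristic. Section 2.13.1 uses the same wording for Week 1 Day 1 mutation status, where it is appropriate. Week 24 MMR is different because treatment determines who falls in each category. If asciminib brings more patients into MMR by Week 24, its responders include patients who would not have responded on bosutinib, and its non-responders are those left behind. The arms are then no longer alike within a category.

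At stake is how the 96-week output is read. An odds ratio among Week 24 responders looks like a statement about durability of response by arm, and this contrast cannot support one. The *overall* odds ratio, if taken from the same model, is also conditional on Week 24 MMR, and it could appear beside the randomized key secondary result with a different value. Meanwhile the quantity the subsection is about, the odds of later MMR by early MMR, is not among the named estimates.

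**Working it through.** **Inputs from the documents.** Week 24 MMR 15% (bosutinib) and 35% (asciminib), with 74 and 148 patients (Section 3.1). Week 96 MMR 30% on bosutinib, with detectable asciminib rates of 50% and 53% (Section 3.2). Not given, hence assumed: the strength of prognosis shared between visits, and early-stop rates by arm.

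**The plan's own figure.** Pooled proportion (0.15 + 2×0.35)/3 = 0.2833.
n(bosutinib) = [1.960×√(0.2833×0.7167×1.5) + 1.282×√(0.15×0.85 + 0.35×0.65/2)]² / 0.20² = 73.2, so 74, and 74 + 148 = 222. Odds ratio (0.35/0.65)/(0.15/0.85) = 3.05. Both agree with Section 3.1.

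**Check 1: latent bivariate normal model.** With latent correlation ρ, P(MMR96 | MMR24 yes) = Φ₂(z24, z96; ρ)/p24 and P(MMR96 | MMR24 no) = (p96 − Φ₂)/(1 − p24).

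| Week 96 MMR, asciminib / bosutinib | ρ | Randomized OR | OR, Week 24 MMR yes | OR, Week 24 MMR no |
|---|---|---|---|---|
| 30% / 30% | 0.3 | 1.00 | 0.78 | 0.85 |
| 30% / 30% | 0.7 | 1.00 | 0.46 | 0.58 |
| 40% / 40% | 0.3 | 1.00 | 0.78 | 0.86 |
| 40% / 40% | 0.7 | 1.00 | 0.43 | 0.62 |
| 50% / 30% | 0.3 | 2.33 | 1.86 | 2.06 |
| 50% / 30% | 0.7 | 2.33 | 1.41 | 1.74 |
| 53% / 30% | 0.3 | 2.63 | 2.11 | 2.33 |
| 53% / 30% | 0.7 | 2.63 | 1.68 | 2.02 |

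For the first row, among Week 24 responders, later MMR is 0.415 on asciminib and 0.476 on bosutinib: (0.415/0.585)/(0.476/0.524) = 0.78.

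**Check 2: no treatment effect after Week 24.** Let logit P(MMR24) = a(arm) + U, calibrated to 15% and 35%, and logit P(MMR96) = c + U with no treatment term, calibrated to 30%. U is a normal prognostic effect. The treatment odds ratios (MMR24 yes / no) are 1.00/1.00 at SD 0, 0.95/0.96 at SD 0.5, 0.84/0.86 at SD 1, 0.60/0.67 at SD 2 and 0.42/0.52 at SD 3. Adding a carry-over effect of Week 24 MMR hardly changes them.

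**Check 3: can the direction reverse?** Assume half the patients have good prognosis (Week 96 MMR 45%) and half poor (15%), whatever the treatment.

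- *Week 24 benefit only in good prognosis* (good/poor: bosutinib 20%/10%, asciminib 60%/10%). MMR24 yes: bosutinib (0.20×0.45 + 0.10×0.15)/0.30 = 0.350; asciminib (0.60×0.45 + 0.10×0.15)/0.70 = 0.407; OR 1.28. MMR24 no: 0.495/1.70 = 0.291 and 0.315/1.30 = 0.242; OR 0.78.
- *Week 24 benefit only in poor prognosis* (bosutinib 25%/5%, asciminib 25%/45%). MMR24 yes: 0.12/0.30 = 0.400 and 0.18/0.70 = 0.257; OR 0.52. MMR24 no: 0.48/1.70 = 0.282 and 0.42/1.30 = 0.323; OR 1.21.

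Either category can therefore go either way with identical later prognosis.

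**Check 4: early stops.** Patients who stop before Week 24 are non-responders at both visits. Using the Check 2 model at SD 1 among those who continue, with bosutinib held at 30% at Week 96, the odds ratio in the MMR24-no category is 0.86 with no stops, 1.01 with 20%/10% stops (bosutinib/asciminib), 1.31 with 30%/10% and 1.81 with 40%/10%. Among Week 24 responders it stays at 0.84 to 0.89. In this calibration the asciminib Week 96 rate rises as well, for example 0.30×0.90/0.70 = 0.386 at 30%/10%. If both arms are held at 30%, the MMR24-no odds ratio stays below 1.

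**Precision.** Expected Week 24 responders: 74×0.15 = 11.1 and 148×0.35 = 51.8. If 70% of them are in MMR later (assumed), SE(log OR) = √[1/(11.1×0.21) + 1/(51.8×0.21)] = 0.72. The 95% interval then extends by a factor exp(1.96×0.72) ≈ 4.1 each way.

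**The case against.** A reader might infer that this output is bound to make asciminib look worse, or its responses less durable, even with no later difference between arms. The documents do not support that. The size of the bias rests on an assumed correlation. At the Week 96 rates in Section 3.2 the same model gives odds ratios of 1.41 to 2.33, attenuated but above 1. Equal Week 96 rates are not the same as no later difference either: asciminib would fall from 35% to 30% while bosutinib doubled from 15% to 30%. Check 2 shows that selection alone can push the odds ratio below 1, and Check 3 that it can push it above 1.

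A reader might also infer that the subsection leaves its own question unanswered. That goes too far. The planned contingency tables, with treatment group included, show later MMR by Week 24 status within each arm, and the model already holds the terms needed. The gap is in which effect estimate is reported.

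The analysis is exploratory and carries no alpha. Randomized comparisons of MMR at Week 96 (Section 2.6) and at other visits including Week 48 (Section 2.7) are planned, as is Kaplan-Meier duration of MMR. All of this stands and limits the consequence.

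Finally, the current text is an addendum dated after the primary database lock, and the analysis has been in the SAP since 2017. Removing a pre-specified output that might disfavour the sponsor's drug could itself be criticised. That is a fair reason to offer labelling as an alternative to deletion.

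**Conclusion.** The concern holds in a limited form. The odds ratios by Week 24 category, and any overall odds ratio from the same model, condition on an outcome that treatment is expected to change. They are not randomized comparisons, and the SAP does not say so. When the two visits share prognosis the usual result is attenuation, or a value below 1 under equal Week 96 rates (about 0.43 to 0.86 for an assumed latent correlation of 0.3 to 0.7). The bias is zero without shared prognosis. It reverses in one category or the other if the Week 24 benefit depends on prognosis, and the MMR24-no odds ratio can exceed 1 if early stops are more frequent on bosutinib. The documents give neither the correlation nor the stop rates, so the direction cannot be fixed from them. With about 11 bosutinib responders expected, the estimate is also imprecise. The reported contrast does not estimate the early-to-late association. The point is minor and worth considering; the primary and key secondary conclusions are untouched.

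**What to change.** From the tables and model already planned in Section 2.14, make the main output, within each arm, the Week 48 and Week 96 MMR rates by Week 24 MMR status, with the odds ratio and 95% CI for Week 24 MMR yes versus no.

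Drop the between-arm odds ratios by Week 24 category and overall, together with the p < 0.1 rule. If they are kept because they were pre-specified, label them as non-randomized and not interpretable as treatment effects or as durability of response by arm.

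Apply the same label to the analyses of post-baseline new BCR-ABL1 mutations in Section 2.13.1. These also report treatment odds ratios within a category formed after randomization, and the only caution there concerns multiplicity.

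The cost is a small wording change to exploratory outputs and one more contrast printed from the same model. No new data are needed. Because the text now postdates the primary database lock, the change should be dated and its reason recorded.
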